HIV VACCINE
TRIALS NETWORK

PROTOCOL

HVTN 303

A Phase 1, Open-Label Clinical Trial to Evaluate Safety, Tolerability, and Immunogenicity of Adjuvanted HIV-1 Fusion Peptide Conjugate Vaccine (VRC-HIVVCP0108-00-VP) Alone or in Prime-Boost Regimens with Adjuvanted HIV-1 Envelope Trimer 4571 (VRC-HIVRGP096-00-VP) and HIV-1 Trimer 6931 (VRC-HIVRGP0106-00-VP) Vaccines in Healthy Adults

DAIDS DOCUMENT ID 38835

IND 028412 HELD BY DAIDS

CLINICAL TRIAL SPONSORED BY

Division of AIDS (DAIDS)
National Institute of Allergy and Infectious Diseases (NIAID)
National Institutes of Health (NIH)
Department of Health and Human Services (DHHS)
Bethesda, Maryland, USA

STUDY PRODUCTS PROVIDED BY

Vaccine Research Center (VRC)
NIAID, NIH, DHHS
Bethesda, Maryland, USA

September 21, 2023

Final
HVTN 303
Version 2.0

HVTN 303 enrolled (vaccinated) its first participant on August 15, 2022, with the goal to enroll 60 participants in the study. As of Dec 20, 2022, 44 participants were enrolled (no enrollments occurred after this date). Part A (Groups 1, 2, 3, 4, and 5) completed enrollment of 15 participants from August 15 to October 14, 2022.

Part B enrolled 29 participants from November 3 to December 20, 2022: Group 6 enrolled 10 ppts, all of whom received 1 vaccination; Group 7 enrolled 10 participants, 5 of whom received 2 vaccinations; Group 8 enrolled 9 participants, 6 of whom received 2 vaccinations. No participants received a 3rd vaccination.

Over time, the PSRT observed trends in local and systemic reactogenicity (grade 3 fever, grade 3 injection site erythema, and/or induration/swelling), unsolicited adverse events (urticaria, rash, and serum sickness), and temporary increases in absolute eosinophil counts (AECs) post-vaccination. Certain of these events resulted in pauses in all vaccinations, and the PSRT requested the HVTN Safety Monitoring Board (SMB) perform an ad hoc review of all safety data. Following this review on January 11, 2023, the SMB recommended that all vaccinations in the study be permanently discontinued, and that participants be continued in safety follow-up, and these recommendations were implemented.

On January 13, 2023, a protocol memo was distributed informing the clinical research sites that all vaccinations in HVTN 303 were permanently discontinued. Vaccinations in Part A were completed on October 14, 2022, and specimen collection for safety labs was completed 4 weeks after the vaccination on November 10, 2022. Discontinuation of vaccinations applied to Part B only. On March 13, 2023, FDA informed DAIDS that the IND has been placed on Clinical Hold and confirmed that all protocol-related activities must cease except for any participant safety follow-up assessments. Safety follow-up assessments, including specimen collection for safety labs, have been conducted for at least 7 months after last vaccination for all participants in Part B and no safety concerns have been identified during this follow-up period.

All participants have been informed using “Dear Participant” letters.

HVTN 303 Protocol sections 1, 2, 3, 6, 7 and 8 have been revised to include language in prior protocol modifications and protocol changes that resulted from the permanent discontinuation of vaccinations in the study. Procedures specified for remaining follow-up visits have been revised.

- For participants in Groups 7 and 8 that received two doses of their respective vaccines, Leukapheresis or 204 ml of blood draw has been added at 10 months +/- 2 month past their last vaccination to investigate immunological outcomes.
- The revised study procedures for Part A participants are shown in new [Appendix B](#) and for Part B participants are shown in new [Appendix D](#).
- The revised visit windows for participants are shown in new [Appendix F](#). New [Appendix H](#) and [Appendix J](#) contains addendums to the sample consent forms for Part A and Part B participants respectively that updates study information and new tables of procedures.

Protocol Signature Page

A Phase 1, Open-Label Clinical Trial to Evaluate Safety, Tolerability, and Immunogenicity of Adjuvanted HIV-1 Fusion Peptide Conjugate Vaccine (VRC-HIVVCP0108-00-VP) Alone or in Prime-Boost Regimens with Adjuvanted HIV-1 Envelope Trimer 4571 (VRC-HIVRGP096-00-VP) and HIV-1 Trimer 6931 (VRC-HIVRGP0106-00-VP) Vaccines in Healthy Adults

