9.1 Adverse events

Unsolicited AEs will be collected over a period of 28 days after each vaccination. All collected AEs are captured in the clinical database on the appropriate case report form (CRF). Clinic staff should evaluate every AE to determine if (1) the AE meets the requirements for expedited reporting (see Section 9.2.1), (2) if the AE meets the criteria for a safety pause/prompt AE review (see Section 9.5), (3) if the AE meets the criteria for an MAAE, and (4) if the AE is a potential immune-mediated medical condition (PIMMC) or an AESI. A sample list of AESIs and PIMMCs is provided in [Appendix M](#).

In addition, a limited set of AEs will be collected and reported for 12 months following any vaccine administration.

- SAEs/EAEs,
- AESIs,
- MAAEs (defined as any AEs leading to an unscheduled visit to a healthcare professional),
- Safety lab-related AEs,
- AEs leading to early participant withdrawal or early discontinuation of study vaccine(s) administration.

AEs will be graded according to the Division of AIDS (DAIDS) Table for Grading the Severity of Adult and Pediatric Adverse Events, Corrected Version 2.1 (<https://rsc.niaid.nih.gov/clinical-research-sites/daids-adverse-event-grading-tables>), with the following exceptions:

- Unintentional Weight Loss is required to be reported as an AE only if it is considered to be potentially deleterious to the participant's health (see HVTN 303 SSP).
- Creatinine is required to be reported as an AE only if it is gradable per the increase from local lab ULN parameter. Do not grade elevated creatinine based on the change from the baseline parameter.
- Do not grade creatinine clearance or estimated glomerular filtration rate (eGFR) based on the change from the baseline parameter. Do not grade on the basis of eGFR if there is clinical concern for kidney injury.

- Injection Site Erythema or Redness and Injection Site Induration or Swelling will not consider surface area and interference with usual social and functional activities, such that:
 - Grade 1 is: 2.5 to < 5 cm in diameter;
 - Grade 2 is: ≥ 5 to < 10 cm in diameter;
 - Grade 3 is: ≥ 10 cm in diameter OR Ulceration OR Secondary infection OR Phlebitis OR Sterile abscess OR Drainage;
 - Grade 4 is: Potentially life-threatening consequences (eg, abscess, exfoliative dermatitis, necrosis involving dermis or deeper tissue)

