Appendix M Adverse events of special interest

AEs of special interest (AESI) for this protocol include but are not limited to potential immune-mediated diseases; representative examples of AESI are listed below.

Updates to AESI will be provided as an appendix to the *HVTN 303 Study Specific Procedures*.

Neuroinflammatory disorders	Musculoskeletal disorders	Skin disorders

 • Cranial nerve disorders, including paryses/paresis (eg, Bell's palsy) • Optic neuritis • Multiple sclerosis • Transverse myelitis • Guillain-Barré syndrome, including Miller Fisher syndrome and other variants • Acute disseminated encephalomyelitis, including site specific variants: eg, noninfectious encephalitis, encephalomyelitis, myelitis, myeloradiculoneuritis • Myasthenia gravis, including Lambert-Eaton myasthenic syndrome • Immune-mediated peripheral neuropathies and plexopathies, (including chronic inflammatory demyelinating polyneuropathy, multifocal motor neuropathy and polyneuropathies associated with monoclonal gammopathy). • Narcolepsy 	
 • Systemic lupus erythematosus and associated conditions • Systemic scleroderma (Systemic sclerosis), including diffuse systemic form and CREST syndrome • Idiopathic inflammatory myopathies, including dermatomyositis • Polymyositis • Antisynthetase syndrome • Rheumatoid arthritis, and associated conditions including juvenile chronic arthritis and Still's disease • Polymyalgia rheumatica • Spondyloarthritis, including ankylosing spondylitis, reactive arthritis (Reiter's Syndrome) and undifferentiated spondyloarthritis • Psoriatic arthropathy • Relapsing polychondritis • Mixed connective tissue disorder 	
 • Psoriasis • Vitiligo • Erythema nodosum • Autoimmune bullous skin diseases (including pemphigus, pemphigoid and dermatitis herpetiformis) • Alopecia areata • Lichen planus • Sweet's syndrome • Localized Scleroderma (Morphea) • Cutaneous lupus erythematosus • Rosacea
		
Metabolic disorders
 
 • Addison's disease • Autoimmune thyroiditis (including Hashimoto thyroiditis) • Diabetes mellitus type I • Grave's or Basedow's disease

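### Version 2.0 names urticaria, rash and serum sickness as observed events but not in the AESI list, and its collection rules conflict on whether late, unattended episodes are recorded

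*Protocol*

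**What the plan says.** The summary at the front of protocol version 2.0 describes trends seen by the safety review team: grade 3 fever, grade 3 injection-site reactions, and "unsolicited adverse events (urticaria, rash, and serum sickness), and temporary increases in absolute eosinophil counts (AECs) post-vaccination". It adds that "Certain of these events resulted in pauses in all vaccinations", after which the SMB reviewed all safety data and recommended a permanent stop with continued safety follow-up. Section 2.11.2 lists rash, urticaria, raised eosinophils and one serum sickness event as observed after Adjuplex-adjuvanted vaccines.

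On collection, section 9.1 states: "Unsolicited AEs will be collected over a period of 28 days after each vaccination". It continues: "In addition, a limited set of AEs will be collected and reported for 12 months following any vaccine administration". That set is SAEs/EAEs, AESIs, medically attended events (MAAEs), safety-lab events, and events leading to withdrawal or discontinuation. Primary endpoint 1 in protocol section 3.1 and SAP section 4 carry the same 28-day limit for all adverse events.

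Appendix M says: "AEs of special interest (AESI) for this protocol include but are not limited to potential immune-mediated diseases". Its examples do not include urticaria, rash or serum sickness, and it sends updates to an appendix of the Study Specific Procedures (SSP).

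The summary says "HVTN 303 Protocol sections 1, 2, 3, 6, 7 and 8 have been revised". Neither that list nor item 2 of the version 2.0 entry in Appendix O, which covers changes made because vaccination ended, includes section 9 or Appendix M.

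**The concern.** The risk text was updated after the stop and the collection text was not. Under section 9.1, a participant who has hives, a rash or serum-sickness-like symptoms more than 28 days after the last dose, and manages them at home, has no assured route into the database. Appendix D, written for this version, points the other way for Part B. Sites following different parts of the same protocol could record different things.

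Safety is the main purpose of the remaining follow-up. The summary reports at least 7 months of it for all Part B participants with no safety concerns identified. For these events that statement is only as informative as the collection behind it: if late, unattended episodes were not recorded, an empty record would not show that none occurred.

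**Working it through.** No sample-size or power figure in the plan depends on this point. The check compares the collection rules and applies date arithmetic.

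**1. Is a non-serious, unattended episode recorded more than 28 days after the last dose?**

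- *Protocol 3.1 and 9.1, SAP 4:* not as a general adverse event. It is recorded only if it is classed as an AESI or leads to withdrawal.
- *Appendix B (Part A):* no. The general adverse-event row has four ticks, which fits Days 0, 7, 14 and 28. The separate AESI/MAAE/SAE row continues to the end.
- *Appendix D (Part B):* yes, on its face. The general adverse-event row has about 15 ticks for Group 6, 22 for Group 7 and 20 for Group 8, separate from the AESI/MAAE/SAE row.

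Group 6 received one dose. Only the visits at Days 0, 7 and 14 fall within 28 days of it, and the next visit is Day 84. About 15 − 3 = 12 ticks therefore lie beyond the window. For two-dose participants in Groups 7 and 8, seven visits (Days 0, 7, 14, 28, 35, 42 and 56) fall within 28 days of a dose, leaving about 22 − 7 = 15 and 20 − 7 = 13 ticks beyond it. Column alignment in the extracted tables is imperfect, but counts of this size cannot fit a 28-day limit.

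**2. Share of planned follow-up outside all-event collection, under section 9.1 alone**

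Inputs: 52 weeks = 364 days for Part A and 56 weeks = 392 days for Part B (section 1.6); a 28-day window per dose; second dose at its Day 28 target.

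- Part A, one dose: (364 − 28)/364 = 336/364 = 92.3%
- Part B, one dose: (392 − 28)/392 = 364/392 = 92.9%
- Part B, two doses: (392 − 56)/392 = 336/392 = 85.7%

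If Appendix D governed, the two Part B figures would not apply.

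**3. How much follow-up remained at version 2.0 (21 September 2023)**

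- Part A enrolled from 15 August to 14 October 2022. Adding 364 days puts target final visits between 14 August and 13 October 2023, so at most 22 days remained.
- Part B enrolled from 3 November to 20 December 2022. Adding 392 days puts target final visits between 30 November 2023 and 16 January 2024, so 70 to 117 days remained.

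**4. Other routes in section 9.1**

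With vaccination over, discontinuation of vaccine can bring in no new events. Letter of Amendment 4 (31 July 2023) removed safety-lab blood collection at future Part B visits, so eosinophil counts no longer give a parallel signal. The footnotes to Appendix D also tell sites to skip future visits without sample collection, which leaves fewer occasions to ask.

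**The case against.** Several stronger conclusions are tempting, and the documents do not support them.

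- *That late episodes are recorded only if serious or medically attended.* Section 9.1 also collects AESIs and "AEs leading to early participant withdrawal or early discontinuation of study vaccine(s) administration". The AESI definition is open, so a site could class serum sickness as one without any change to the list.
- *That the events were never added to the AESI list.* This can be shown only for Appendix M. Updates go to the SSP, which is not among the documents.
- *That follow-up cannot show recurrence.* Appendix D appears to ask for general adverse events in Part B. Interim history, targeted examination and concomitant medications, including non-prescription drugs, also continue at follow-up visits, so self-treated hives might leave a trace.
- *That these three events stopped the trial.* The summary also lists grade 3 fever and grade 3 local reactions and does not say which events were decisive.

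It is also fair to say that the documents report no late or recurrent episode, and that little prospective follow-up remained at version 2.0.

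These objections narrow the point but do not remove it. Appendix D does not cure the gap: it contradicts sections 3.1 and 9.1 and SAP section 4, and it adds nothing for Part A. An open list leaves classification to each site. A trace in the medication record is not a recorded adverse event.

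**Conclusion.** The point holds in a limited form. Two defects are documented: Appendix M omits three events that version 2.0 itself reports as observed, and sections 3.1 and 9.1 with SAP section 4 disagree with Appendix D on what is recorded in Part B more than 28 days after a dose. As a result, late, non-serious, unattended episodes may not be captured reliably or uniformly. The absence of safety concerns in Part B follow-up cannot be interpreted for these events until it is known which rule sites followed.

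Under section 9.1 alone, the affected share of planned follow-up is about 92% in Part A and 86% to 93% in Part B. For Part B it could be far smaller if Appendix D was followed. Prospective gain is limited to at most 22 days in Part A and 70 to 117 days in Part B, so much of the remedy is retrospective. The conclusion rests on the SSP not having already added these events, which cannot be checked here, and on the extracted tick rows being broadly right.

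**What to change.** 1. Reconcile protocol sections 3.1 and 9.1 and SAP section 4 with Appendix D, so that one stated rule says which adverse events are recorded more than 28 days after a dose.
2. Name urticaria, generalised rash, and serum sickness or serum-sickness-like reaction as AESIs in Appendix M for all groups, whether or not medically attended, or confirm that the SSP appendix already does so.
3. Ask about these events at each remaining scheduled visit. Ask once retrospectively about the period since Day 28 after the last dose, recording onset date and doses received, and flag these answers as retrospective.
4. State in the final safety report which collection rule was applied, by part, before interpreting the absence of safety concerns in follow-up.

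The cost is one list entry, aligned wording in four places, and one question at visits already scheduled. The downside is recall error over many months in the retrospective answers, which is why they should be kept distinguishable. Exclusion criterion 17 also refers to AESIs, but enrollment is closed, so a longer list would not affect eligibility.

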1.1 Title

A Phase 1, Open-Label Clinical Trial to Evaluate Safety, Tolerability, and Immunogenicity of Adjuvanted HIV-1 Fusion Peptide Conjugate Vaccine (VRC-HIVVCP0108-00-VP) Alone or in Prime-Boost Regimens with Adjuvanted HIV-1 Envelope Trimer 4571 (VRC-HIVRGP096-00-VP) and HIV-1 Trimer 6931 (VRC-HIVRGP0106-00-VP) Vaccines in Healthy Adults.

1.2 Design

This is a phase 1, open-label, dose-escalation study to evaluate the dose, safety, tolerability and immunogenicity of adjuvanted HIV-1 Fusion Peptide (FP) conjugate vaccine (FP8v1-rTTHC) alone or in prime-boost regimens with adjuvanted HIV-1 Trimer 4571 ~~and adjuvanted HIV-1 Trimer 6931~~. The primary hypothesis is that FP8v1-rTTHC, HIV-1 Trimer 4571, and HIV-1 Trimer 6931 adjuvanted vaccines are safe and tolerable when administered alone and when co-administered with HIV-1 Trimer 4571, in prime-boost regimens.

1.3 Study products

- FP8v1-rTTHC (FP conjugate vaccine) is an HIV-1 fusion peptide conjugated to recombinant tetanus toxoid heavy chain fragment C (rTTHC) via sulfo-SIAB chemical linker. FP8v1 corresponds to the amino-terminal eight residues of the most prevalent HIV fusion peptide sequence. FP conjugate vaccine will be provided at a 1-milligram (mg)/milliliter (mL) concentration in 3-mL glass vials filled to 0.7 mL.
- HIV-1 Trimer 4571 (Trimer 4571) is a synthetic soluble HIV-1 envelope product that consists of an HIV-1 envelope (Env) trimer variant, derived from clade A, strain BG505. Trimer 4571 is provided at a 500-mcg/mL concentration in 3-mL glass vials filled to 1.2 mL
- HIV-1 Trimer 6931 (Trimer 6931) is a synthetic soluble HIV-1 envelope product that consists of an HIV-1 envelope (Env) trimer variant, derived from consensus clade C sequence (ConC). Trimer 6931 will be provided at a 1-mg/mL concentration in 3-mL glass vials filled to 1.2 mL.
- Adjuplex is the adjuvant and will be provided in a sterile, pyrogen-free, homogeneous suspension at 0.7 mL in 3-mL glass vials. Adjuplex will be mixed with study products in the pharmacy during preparation prior to vaccination at a 20% dose by volume.

- PBS (labeled as Phosphate Buffered Saline pH 7.2): Diluent.

1.4 Study population

Healthy adults aged 18 to 50 years, inclusive.

1.5 Study plan and schema table

This study has two parts. Part A will evaluate the safety, tolerability, and immunogenicity of single doses of the FP conjugate, Trimer 4571 and Trimer 6931 vaccines, in a dose-escalation design. Each product must be assessed as safe prior to use in Part B. Trimer 4571 with alum adjuvant has been previously evaluated in humans but will be tested in Part A with Adjuplex. Part B will evaluate the safety, tolerability, and immunogenicity of FP conjugate prime, Trimer 4571 prime, or an FP plus Trimer 4571 prime, all followed by subsequent doses of Trimer 4571, ~~Trimer 6931 and both Trimmers combined~~. Study vaccines will be administered intramuscularly (IM) via needle and syringe in two injection sites. The study schema is in [Table 1-1](#) below:

Table 1-1 Schema

Part A: Dose Escalation**											
Group	N	W0	W4	W8***	W12***	W20***	W24***	W32***	W36***	W44***	W48***
1	3	25 mcg FP conjugate vaccine									
2	3										
3	3	100 mcg Trimer 6931									
4	3	200 mcg Trimer 6931									
5	3	200 mcg Trimer 4571									
Part A Total	15*										
Part B: Prime Boost Regimen**											
Group	N	W0	W4	W8***	W12***	W20***	W24***	W32***	W36***	W44***	W48***
6	± 10	200 mcg Trimer 4571			200 mcg Trimer 4571		200 mcg Trimer 6931		100 mcg Trimer 4571 + 100 mcg Trimer 6931		100 mcg Trimer 4571 + 100 mcg Trimer 6931
7	± 10	200 mcg FP conjugate vaccine	200 mcg FP conjugate vaccine	200 mcg FP conjugate vaccine	200 mcg Trimer 4571		200 mcg Trimer 4571		200 mcg Trimer 6931		200 mcg Trimer 4571 + 100 mcg Trimer 6931
8	± 9	200 mcg FP conjugate vaccine + 200 mcg Trimer 4571	200 mcg FP conjugate vaccine + 200 mcg Trimer 4571	200 mcg FP conjugate vaccine + 200 mcg Trimer 4571		200 mcg Trimer 6931		100 mcg Trimer 4571 + 100 mcg Trimer 6931		100 mcg Trimer 4571 + 100 mcg Trimer 6931	
Part B total	45[§]29										
Overall Total	60[‡] 44										

Table 1-1 Footnotes:

**Adjuplex adjuvant will be mixed with all study products in Part A and Part B at 20% by volume in the pharmacy during product preparation for all vaccinations. Once mixed, all study injections will be divided into 2 syringes, and each syringe will be administered intramuscularly to one of the deltoids.

* In Part A, up to 20 participants may be enrolled if needed for safety evaluations. Additional participants may be enrolled to ensure the availability of 2-week safety data from at least 3 participants per group. Refer to the HVTN 303 Study Specific Procedures (SSP) for further details.

§ In Part B, up to 50 participants may be enrolled if needed for safety evaluations. Additional participants may be enrolled to ensure the availability of 2-week safety data from at least 15 participants per group. Refer to the HVTN 303 SSP for further details.

† Total up to 70 participants can be enrolled if needed for safety evaluations. Refer to the HVTN 303 SSP for further details.

Notes:

***Vaccination in Part B starting from Week 8 onwards did not take place.

Actual Ns for Group 6, 7 and 8 were 10, 10 and 9 respectively. In Part B total 29 participants were enrolled.

Part A of the study may begin with direct enrollment of participants into the following groups simultaneously:

- Group 1 with no more than 1 participant enrolled per day for the 3 participants.
- Group 3 with no more than 1 participant enrolled per day for the 3 participants.

After Groups 1 and 3 have been fully enrolled, the study will be placed on a safety hold. No additional enrollments will proceed until the Protocol Safety Review Team (PSRT) has determined it is safe to do so. Once all of the reactogenicity and 2-week safety data from at least 6 participants have been submitted to the database, the PSRT must assess the accumulated product-specific data as showing no significant safety concerns before proceeding with enrollment of Groups 2, 4 and 5. If the PSRT has determined it is safe to proceed after reviewing data from Groups 1 and 3, the following groups may begin simultaneously:

- Group 2 with no more than 1 participant enrolled per day for the 3 participants
- Group 4 with no more than 1 participant enrolled per day for the 3 participants
- Group 5 with no more than 1 participant enrolled per day for the 3 participants

Once Groups 2, 4 and 5 have been fully enrolled, the study will be placed on a safety hold before proceeding with Part B. Once all of the reactogenicity and 2-week safety data from at least 9 participants have been submitted to the database, the PSRT must assess the accumulated product-specific data as showing no significant safety concerns before proceeding with enrollment of Part B.

Part B enrollments may only proceed if no safety concerns have been identified for any of the product administrations in Part A of the study.

If at any time there is insufficient data to conduct a formal PSRT Safety Review because of participant discontinuations from the study before sufficient data are collected, then additional participants may be enrolled into that group to acquire the requisite data on the required number of participants specified above.

Moreover, the PSRT may recommend additional participants be enrolled into a given treatment group if additional safety evaluations are requested.

Consultation with the HVTN Safety Monitoring Board (SMB), Institutional Review Board (IRB) and Food and Drug Administration (FDA), if needed, as specified by study pause criteria (per Section 9.5.1), will occur if indicated.

